#### Muscle thickness

The muscle thickness of the Vastus Lateralis and Rectus Femoris of each leg will be determined by B-Mode Ultrasonography (Healcerion, UK), this will be conducted by a qualified member of the research team with the appropriate skills and training. The measurements will be conducted at 50% of femur length, determined by the distance between knee joint space and greater trochanter as defined by palpation. Muscle thickness will be quantified using ImageJ (NIH, USA) post-hoc. Images will be saved on the Healcerion system as anonymised codes, i.e. SPRESS-1-Pre. Images will then be anonymised and coded by another member of the team before being analysed blindly by [name] (Co-I), using ImageJ Software (NIH, USA)

## 5 x sit to stand

In-patient participants will be timed for how long it takes them to complete 5x sit to stand. Participants will be allowed to use their ambulatory aides if required and this noted. Participants will have an investigator near them to prevent an adverse falls or loss of balance. Where this takes longer than 60s, the number of complete movements and the time it took for those will be recorded. Participants will be asked to complete this 3x if possible, with sufficient rest in between each attempt, to enable an average to be taken.

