#### **Research objectives:**

### **Primary Objectives:**

The primary objectives are to quantify changes in the following in response to 12 sessions (2x per week for 6 weeks) of using the S-Press device supervised by a Physiotherapist. The primary outcomes are to assess:

- Functional improvements using the 5x sit to stand test.
- Morphological changes, measuring muscle thickness of the Vastus Lateralis and Rectus Femoris muscle using B-Mode ultrasound.
- Any safety issues with *S-Press* use with older users.
- Perceptions of usability of the S-Press with older adult users and care givers.

Short title: S-Press

Sponsor code: JT Rehab-01

IRAS number: 251647

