### Justification for NHS staff involvement and numbers:

The role of the NHS physio team is to enable the fastest recovery of sit to stand and transfer ability to enable speedy discharge of in-patient's home to a familiar environment. Strengthening exercise provision is a standard treatment provided for this purpose, limited in many Trusts by availability of appropriate equipment. Provision of several free exercise devices per site that can deliver effective, specific, sit to stand muscle strengthening for the length of the trial, is a good benefit to the staff and the patients. The number of patient participants is being kept at a low level of 4 patients per site. Senior management have buy-in from the staff and have appropriate safe staffing levels available to participate in the study. Number of exercise sessions will be twice a week to follow national recommendations for strength training, for approximately 30 minutes. Patients are seen daily on the ward for therapy intervention including strengthening and mobility work. Daily, 30-minute sessions are the gold standard for daily therapy interventions.

No specific number of staff participants has been set to be recruited, so there is no added pressure for participation. There will be 2 devices per site available so a minimum of 2 staff members per site is preferred for the study to maximise the benefit and use of the S-Press and for feedback.

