## Physiological Assessments (Quantitative Data)

These assessments will be conducted at baseline (start) and at the end of the intervention period (6 weeks). Post testing will be conducted 48-72 hours post final exercise session to allow for any fluid changes within the muscle to subside and minimise fatigue of participants. There will be a familiarisation session for all participants prior to completing the baseline assessments to minimise any learning effects of the assessments.

Short title: S-Press

Sponsor code: JT Rehab-01

IRAS number: 251647

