#### **Exercise Sessions**

First, participants will be asked to warm up supervised by the physiotherapist, this will incorporate some low intensity range of movement exercise and light stretching.

Staff participants will set up the patient participant using the S-Press protocol for set up. Patients can remain on the bed or in the chair so will not require transferring or position change by the staff for use.

Short title: S-Press

Sponsor code: JT Rehab-01

IRAS number: 251647

Initial assessment of appropriate resistance level will be examined at the beginning of the first session, by assessing the patient participants 1 repetition max (1RM) level (maximum resistance level ability - Instructions stated in set up protocol).

Participants will then complete 3 sets of 10 repetitions on each leg firstly for the knee extensors and then the knee flexors. The S-Press allows both Concentric and Eccentric muscle actions, so muscle groups are performed independently. A guide of 1 minute's rest will be provided in between sets and legs, although more rest will be allowed if required by the participants. The amount of time per exercise session will be approximately 30 minutes.

Blood pressure and heart rate will be measured before the exercise session begins, mi-way through and again at the end of the session. This is to ensure that there is maintenance of optimal levels of blood pressure and heart rate and monitoring of any adverse effects. These measurements are regularly taken by therapy staff to assess their patients' conditions before and during physical intervention.

Data from the assessments will be analysed using paired t-tests. As this trial is an efficacy and feasibility trial descriptive statistics (mean, standard deviation and % Change) will be calculated. In addition, Cohen's D will be used to determine effect sizes to quantify the magnitude of any differences in variables. A p value of p<0.05 will be used to determine significance, with effect size of <0.2=small; 0.5= moderate; >0.8 large.

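### The 5x sit to stand can be timed under different walking-aid support at baseline and at 6 weeks, yet the two times are compared as a plain paired difference

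*Protocol*

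**What the plan says.** Under Primary Objectives, the first item in the list of outcomes is "Functional improvements using the 5x sit to stand test". Physiological Assessments (Quantitative Data) places the assessments at baseline and at the end of the 6 weeks.

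The section 5 x sit to stand defines the measure: "In-patient participants will be timed for how long it takes them to complete 5x sit to stand". On support it says: "Participants will be allowed to use their ambulatory aides if required and this noted". On repeats it says: "Participants will be asked to complete this 3x if possible, with sufficient rest in between each attempt, to enable an average to be taken".

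The analysis paragraph at the end of Exercise Sessions says: "Data from the assessments will be analysed using paired t-tests", with mean, standard deviation, percentage change and Cohen's d, and "A p value of p<0.05 will be used to determine significance". It gives the noted aid use no role.

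The design is single-arm, and the sample size section says that no control group was required. The section on NHS staff involvement describes daily ward therapy, including strengthening and mobility work, and says: "The role of the NHS physio team is to enable the fastest recovery of sit to stand and transfer ability".

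**The concern.** A paired difference measures change in the participant only if the test is the same on both occasions. Here the support may differ. A participant who pushes up through a frame at one visit and stands without it at the other has done two different tasks, and the difference in time reflects the aid as well as the legs.

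Two cases show the effect. Someone who takes 25 s with a frame at baseline and 25 s without one at 6 weeks has plausibly improved but scores zero change. Someone tested without an aid at baseline and with one at 6 weeks may score faster with no gain in leg function.

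The setting makes switching plausible, because these are in-patients whose therapy aims to restore the very ability being timed. With no control group, no comparator can absorb a general drift in aid use. The outcome is also part of the success criteria in the background section, which ask for clinically significant improvement in sit to stand ability. No threshold is given there against which a shift in the mean could be judged.

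**Working it through.** **1. Is support held constant anywhere?** Four places could do so.
- 5 x sit to stand: permits aids according to need and records them. It sets no rule across visits or across the attempts that are averaged.
- Physiological Assessments: fixes the timing only.
- Familiarisation: offers practice to reduce learning effects and is silent on support.
- Analysis paragraph in Exercise Sessions: a paired t-test, with no rule for pairs whose support changed.

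The gap is therefore open in the protocol text.

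**2. Number of completers.** The protocol's own figure reproduces: the recommended minimum of 12, inflated for 20% attrition, is 12 / (1 − 0.20) = 15, the lower end of the 15-20 target. At the upper end, 20 × 0.80 = 16. So 12 to 16 completers are expected.

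**3. Formula for the bias.** Let the change be the 6-week time minus the baseline time, s the seconds by which an aid shortens the test, a the number who go from aided to unaided, u the number who go the other way, and n the number of completers. Then:

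bias in mean change = s × (a − u) / n

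A positive value makes the group look slower and hides a gain; a negative value mimics one.

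**4. Illustrative range.** The protocol gives none of s, a or u. Assume s = 2 to 8 s and a net 2 to 6 switchers.

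| n | Net 2, s = 2 s | Net 4, s = 5 s | Net 6, s = 8 s |
|---|---|---|---|
| 12 | 4/12 = 0.33 s | 20/12 = 1.67 s | 48/12 = 4.0 s |
| 16 | 4/16 = 0.25 s | 20/16 = 1.25 s | 48/16 = 3.0 s |

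Cancellation matters. Four switchers split 2 and 2 give zero. Split 3 and 1 with s = 5 s and n = 12, they give 5 × 2 / 12 = 0.83 s.

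**5. Likelier direction: aided to unaided.** Assume an SD of change of 5 s and a two-sided test (the protocol does not state sidedness). For 80% power a paired t-test needs a mean change of about 0.89 SD at n = 12 and 0.75 SD at n = 16.
- n = 12: 0.89 × 5 = 4.45 s. After a loss of 1.67 s, 2.78 s remains, or 2.78 / 5 = 0.56 SD.
- n = 16: 0.75 × 5 = 3.75 s. After a loss of 1.25 s, 2.50 s remains, or 0.50 SD.

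A true gain just large enough for 80% power would then fall well short of it.

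**6. Reverse direction: unaided to aided.** Simulation with no true change, SD of change 5 s, every switch in this direction, and 40,000 runs per scenario. The nominal rate of a false significant result in the faster direction is 2.5%.
- n = 12: 4% to 49% over the range in step 4; 13% for 4 switchers and 5 s.
- n = 16: 4% to 39%; 12% for 4 switchers and 5 s.

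These rates are upper illustrations, because they assume one-way switching in the less likely direction.

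**The case against.** The strongest reply is that aid use is recorded. Switched pairs can be identified, unchanged pairs analysed separately and the number of switches reported, and such analyses commonly belong in an SAP, which is not at hand. This largely stands. A reader might infer that the damage cannot be repaired at all; the documents do not support that, since participants with unchanged support do have matched times. What no SAP can supply is a like-for-like time for those who switched. Leaving them out of 12 to 16 completers costs precision and may remove those whose function changed most. How the test is performed remains a protocol matter.

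The direction also weakens the alarm. If ward therapy works, most switches should be from aided to unaided, which counts against the device. A reader might take the false-positive rates above as the expected harm, but they describe the less plausible switch.

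Two further inferences go beyond the text. One is that changes of aid come from ward care and not from the S-Press: improving sit to stand, transfers and walking is also the device's stated purpose, and a single-arm study cannot separate the two. The other is that support will vary among the three attempts at one visit: the protocol does not forbid this, but nothing in it suggests that it will happen.

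Finally, that an aid shortens the test by relieving the legs is an assumption, as the protocol does not describe how aids are used in it. If an aid slowed a participant, the direction would reverse, but the two times would still not be comparable.

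**Conclusion.** The point holds as a gap in how a primary outcome is measured. The protocol allows support to differ between the two times it pairs, and no other section closes this. The likelier effect in recovering in-patients is to mask benefit; a spurious benefit is possible but needs the reverse switch.

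No size can be given from the documents. The 0.25 to 4.0 s range rests on assumed switching, an assumed aid effect and a net movement in one direction; the power and error figures add an assumed SD of change of 5 s. With balanced switching the mean would not move, though the differences would be noisier. The conclusion that the test condition should be fixed depends on none of these values. The change is worth making because it is cheap before testing and only partly recoverable afterwards.

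**What to change.** In the section 5 x sit to stand, replace the present sentence on aids with a rule to this effect:

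- The support used is recorded for every attempt, at baseline and at 6 weeks.
- Where the participant can safely do so, the 6-week attempts that enter the paired analysis use the same support as at baseline.
- If the aid is no longer needed at 6 weeks, one further unaided attempt is recorded and reported descriptively.
- A participant who cannot repeat the test with the baseline support is tested with the support needed, stays in the reported results, and is counted as worsened beside the mean change. Silently dropping these times would remove the worsened cases and tilt the mean towards improvement.

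In the analysis paragraph, or in an SAP, add the number whose support changed in each direction and a sensitivity analysis restricted to pairs with unchanged support. That analysis should be read together with the count of worsened participants, since it leaves them out. If testing has already taken place, these two additions can still be made from the aid use that was noted.

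Cost: a few sentences, one extra field on the data sheet, and one extra attempt for the few participants who no longer need their aid.

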#### **Exercise Sessions**

First, participants will be asked to warm up supervised by the physiotherapist, this will incorporate some low intensity range of movement exercise and light stretching.

Staff participants will set up the patient participant using the S-Press protocol for set up. Patients can remain on the bed or in the chair so will not require transferring or position change by the staff for use.

Short title: S-Press

Sponsor code: JT Rehab-01

IRAS number: 251647

Initial assessment of appropriate resistance level will be examined at the beginning of the first session, by assessing the patient participants 1 repetition max (1RM) level (maximum resistance level ability - Instructions stated in set up protocol).

Participants will then complete 3 sets of 10 repetitions on each leg firstly for the knee extensors and then the knee flexors. The S-Press allows both Concentric and Eccentric muscle actions, so muscle groups are performed independently. A guide of 1 minute's rest will be provided in between sets and legs, although more rest will be allowed if required by the participants. The amount of time per exercise session will be approximately 30 minutes.

Blood pressure and heart rate will be measured before the exercise session begins, mi-way through and again at the end of the session. This is to ensure that there is maintenance of optimal levels of blood pressure and heart rate and monitoring of any adverse effects. These measurements are regularly taken by therapy staff to assess their patients' conditions before and during physical intervention.

Data from the assessments will be analysed using paired t-tests. As this trial is an efficacy and feasibility trial descriptive statistics (mean, standard deviation and % Change) will be calculated. In addition, Cohen's D will be used to determine effect sizes to quantify the magnitude of any differences in variables. A p value of p<0.05 will be used to determine significance, with effect size of <0.2=small; 0.5= moderate; >0.8 large.

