Leg muscle weakness, especially knee-extensor strength, is associated with increased falls risk (Tinetti 1988; Wolfson 1995) and decrease in function (Van Roie et al., 2011). Leg strength gain is associated with improvements in sit to stand, gait, transfers, stair climbing and confidence (Chandler 1998). A study is needed to assess if providing PRE to older adults via use of the S-Press device has a beneficial effect on muscle strength and if this translates into functional task improvement.

PPI using expert patients and clinicians from three NHS Trusts have participated in focus groups. A national proof of market study run by NIHR Devices for Dignity has shown a positive response to the S-Press concept and recognition of its potential value. These discussions have all contributed to the final S-Press design decisions and features. In-patient feedback on physiotherapy interventions describes a feeling of achievement and a sense of doing 'real physio' when using exercise devices, as compared to 'just walking'. Competition between patients is also known to be beneficial and encourages participation and improvement; all achievable with S-Press use.

Success criteria will be to show clinically significant improvements in lower limb muscle size, sit to stand ability of 15 - 20 older adults, and the views on use and acceptability with users and staff, following 6 weeks of training with the S-Press. Evidence that this improvement in lower limb muscle size and strength transfers to an improvement in a range of selected validated functional skills and sufficient user qualitative feedback will allow CE marking of the device enabling further NHS studies.

The project lead and S-Press inventor is a physiotherapist with 22 years of older people's rehabilitation experience. Researchers from Sheffield Hallam University will devise, run, and analyse the quantitative data from the study. The qualitative element of the real-world evaluation will be

Short title: S-Press

Sponsor code: JT Rehab-01

IRAS number: 251647

performed and analysed by the research team at Northamptonshire Healthcare NHS Trust. Devices for Dignity have previously provided proof of market evidence and will provide regulations assistance, health economics and commercialisation to enable CE marking. S-Press development has been funded by Versus Arthritis.

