### Sample size justification:

For the study we will aim to recruit 15 - 20 NHS in-patient participants across the 4 sites. Sample size aligns with previous research studies using similar methodology (e.g., Dibble et al. 2006; Alkner, et al., 2004; Frontera, et al., 1988; Fiatarone, et al., 1990; Grimby, et al., 1985; Pyka, et al. 1994; Hagerman et al. 2000; Hepple, et al. 1997)

Typical exercise training studies of this length have 10-15 participants per arm of the trial. This would conventionally include a control group. As this is a feasibility trial, the advice from our RDS was that a control group was not required. An N of 12 has been recommended as a minimum number of participants per group to be recruited for a clinical trial where there is no prior information to guide sample size (Julious 2005). This figure is suggested to represent the lower threshold required to estimate the standard deviation of measures with adequate precision. We aim to recruit 15-20 participants to the study to allow for a predicted 20% attrition rate.

This low number of patient participants per site will provide a low burden for the staff participants.

Short title: S-Press

Sponsor code: JT Rehab-01

IRAS number: 251647

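### Four muscle-thickness values can each be tested at p<0.05, with no rule for turning them into the single muscle-size result that the success criterion needs

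*Protocol*

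**What the plan says.** The Protocol lists two quantitative primary outcomes under Primary Objectives. One is functional: "Functional improvements using the 5x sit to stand test". The other is structural: "Morphological changes, measuring muscle thickness of the Vastus Lateralis and Rectus Femoris muscle using B-Mode ultrasound".

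The Muscle thickness section adds the legs: "The muscle thickness of the Vastus Lateralis and Rectus Femoris of each leg will be determined by B-Mode Ultrasonography". Two muscles in two legs make four thickness values per participant at each of the two assessments.

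The analysis paragraph at the end of Exercise Sessions says "Data from the assessments will be analysed using paired t-tests" and "A p value of p<0.05 will be used to determine significance". It also plans means, standard deviations, percentage changes and Cohen's d. It does not state whether tests are one- or two-sided.

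The Background sets the aim: "Success criteria will be to show clinically significant improvements in lower limb muscle size, sit to stand ability of 15 - 20 older adults", together with the views of users and staff. Muscle size appears there as one item. The Protocol nowhere averages legs, combines the two muscles or names a lead measurement. For sit to stand it does give such a rule: up to three attempts are averaged.

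**The concern.** The success criterion asks one question about muscle size, and the measurements can give four answers. With no combining rule fixed beforehand, the team could find one muscle in one leg below 0.05, the other three not, and still report that muscle size improved. With four chances, that conclusion is more often wrong than the 0.05 threshold suggests.

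This matters because the Protocol intends the muscle-size result to support CE marking and further NHS studies. An isolated single-site finding would be weak evidence of hypertrophy. Readers could not tell whether that site was chosen before or after the results were seen.

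**Working it through.** **Inputs from the Protocol**
- Thickness values per participant: 2 muscles × 2 legs = 4 (Primary Objectives; Muscle thickness).
- Test and threshold: paired t-test, p<0.05 (Exercise Sessions).
- Sample size: a minimum of 12, 20% attrition, 15 to 20 recruited (Sample size justification).

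**Assumptions, not in the Protocol**
- Tests are two-sided, so each has a 2.5% chance of a false improvement.
- The four thickness changes are normally distributed with a common correlation r between 0 and 0.8.

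**Step 1: the Protocol's own figure.** 12 / (1 − 0.20) = 15, the lower end of the recruitment range. At the upper end, 20 × 0.80 = 16. The analysis would therefore have about 12 to 16 pairs.

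**Step 2: any one of four tests, independent changes (r = 0).**
- False improvement: 1 − 0.975⁴ = 9.6%.
- Either direction: 1 − 0.95⁴ = 18.5%.

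**Step 3: correlated changes.** Paired t-tests were simulated with no true change, at 12 and 16 pairs.

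| Correlation r | Any of four, improvement | Any of four, either direction |
|---|---|---|
| 0 | about 10% | about 19% |
| 0.8 | about 6% | about 12% |
| One test, for comparison | 2.5% | 5% |

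The number of pairs makes almost no difference, because each t-test holds its own level. As r approaches 1, the four tests become one and the rate falls to 2.5%.

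**Step 4: legs averaged, two muscles still tested separately.** With independence, 1 − 0.975² = 4.9% for a false improvement. With correlation the rate falls to about 4%. The range is therefore about 4 to 5%.

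**Step 5: one value per participant, tested once.** The false-improvement rate is 2.5%.

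**Step 6: the joint criterion.** Suppose muscle size and sit to stand must both improve, and neither has truly changed. Even allowing any one of the four thickness tests, the chance of a false joint success with independent outcomes is 0.096 × 0.025 = 0.24%. With the modest correlation to sit to stand assumed here (0.2), it stays below 1%.

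**The case against.** **The count of tests is inferred.** The Protocol measures each leg but does not say that each leg is tested separately, and averaging legs is ordinary practice. This stands, and it is why the rate is stated conditionally. Averaging legs would still leave two muscles and one muscle-size question, at about 4 to 5% (step 4).

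**A statistical analysis plan may settle it.** That is possible, and a combining rule is often placed there. But the Protocol itself fixes the test, the threshold and the success criterion, and gives an averaging rule for sit to stand and none for thickness.

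**Success is not defined as p<0.05.** The Background asks for clinically significant improvement, and the planned effect sizes and percentage changes would help to expose an isolated result. This also stands. The Protocol does not say that one significant leg meets the criterion; it only fails to exclude that reading.

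**A stronger reading is tempting.** A reader might add sit to stand as a fifth test and infer that the trial has a 16 to 23% chance of false success (1 − 0.95⁵ = 22.6% if independent). The documents do not support this. That figure counts significant worsening as success, and it treats any one of five results as enough, whereas the Background lists muscle size and sit to stand together. The Protocol also promises no familywise 5% level, and it describes itself as an efficacy and feasibility study.

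A reader might also fear that left and right legs will be pooled as independent observations. The Protocol does not propose that analysis.

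**Conclusion.** The point holds in a narrow form and is minor. The Protocol does not say how four thickness values become one muscle-size result. If any one significant increase is taken as enough, the muscle-size conclusion has a false-improvement rate of about 6 to 10% instead of 2.5%, or 12 to 19% instead of 5% if both directions count.

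These figures rest on two-sided tests, 12 to 16 pairs, correlations of 0.8 down to 0, and the any-one-of-four reading. A higher correlation would shrink the excess.

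When nothing has changed, the overall success criterion is not inflated if muscle size and sit to stand must both improve. The weakness remains where sit to stand truly improves and muscle does not, because the muscle-size component then decides the claim.

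**What to change.** In the analysis paragraph of Exercise Sessions, add:

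- For each participant and visit, thickness is averaged over the two legs for each muscle.
- The muscle-size conclusion rests on one pre-specified value, tested once by paired t-test at p<0.05. This is either the mean of the two leg-averaged muscles or one named lead muscle. The choice is made before the data are seen.
- Changes in single legs and single muscles are reported descriptively with 95% confidence intervals.

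This takes a few sentences and no new data. The cost is that a change confined to one leg or one muscle becomes descriptive only, and averaging the two muscles merges measurements that the Primary Objectives name separately.

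There is also a gain in precision. With equal variances and a common correlation r, the standard error of the mean of four values relative to a single value is √((1 + 3r)/4), which is 0.79 at r = 0.5 and 0.92 at r = 0.8. Both r values are assumptions.

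A formal rule that muscle size and sit to stand must both reach significance is not needed to settle this point. It would cost power, so it should be decided separately.

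### The Cohen's d scale calls any value below 0.2, including zero, small, makes moderate a single point, and leaves the rest of 0.2 to 0.8 unlabelled

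*Protocol*

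**What the plan says.** The analysis text is the last paragraph of the protocol section Exercise Sessions. It sets the test: "Data from the assessments will be analysed using paired t-tests". It also asks for the mean, standard deviation and percentage change. It then gives the effect size its purpose: "Cohen's D will be used to determine effect sizes to quantify the magnitude of any differences in variables". The labels follow in the same sentence as the significance level: "A p value of p<0.05 will be used to determine significance, with effect size of <0.2=small; 0.5= moderate; >0.8 large".

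The protocol does not say which standard deviation divides the mean change. It gives no other bands, no category for a negligible effect, and no rule for values between the cut-points.

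The number of participants comes from the section Sample size justification, which gives a recommended minimum of 12 and continues: "We aim to recruit 15-20 participants to the study to allow for a predicted 20% attrition rate".

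**The concern.** A scale that assigns words to an effect size should give each value one word and should be able to say that nothing happened. This one does neither. *Small* is a range with an upper limit of 0.2 and no lower limit, so it takes in zero. *Moderate* is one number. *Large* begins above 0.8. The values in between, where a training study of this kind could easily land, have no word.

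What is at stake is the wording of the results. The data are meant to support CE marking, and an absent change reported as a small effect reads in the device's favour. For mid-range values the analyst must invent a label after seeing the data. Two analysts could describe d = 0.35 or d = 0.65 differently and both claim to have followed the protocol.

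**Working it through.** **Step 1: apply the rule as written.** The scale is a convention, so there is no calculated figure to reproduce. Applied to the absolute value of d:

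| Absolute d | Label under the protocol's rule |
|---|---|
| 0, 0.05, 0.19 | small |
| 0.20, 0.30, 0.49 | none |
| 0.50 | moderate |
| 0.51, 0.60, 0.70, 0.80 | none |
| 0.81 | large |

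There are 61 two-decimal values from 0.20 to 0.80, and 60 of them have no label. This step rests on the text alone.

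**Step 2: number of completers.** Recruitment of 15 to 20 with 20% attrition gives 15 × 0.8 = 12 to 20 × 0.8 = 16. In the other direction, 12 / (1 − 0.2) = 15, so the lower recruitment figure agrees with the recommended minimum of 12.

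**Step 3: how often the rule would misdescribe or fail.** Assumption: d = mean change / SD of change, with normally distributed changes. Then t = d × √n has n − 1 degrees of freedom. It is central if there is no true change, and otherwise noncentral with parameter (true d) × √n.

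*No true change.* P(|d| < 0.2) = P(|t| < 0.2 × √n).
- n = 12: 0.2 × √12 = 0.693 with 11 df, giving 49.7%.
- n = 16: 0.2 × √16 = 0.800 with 15 df, giving 56.4%.

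So about half of the results from an ineffective programme would be called a small effect.

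*True change present.* P(0.2 ≤ |d| ≤ 0.8) is the noncentral t probability that |t| lies between 0.2 × √n and 0.8 × √n. These limits are 0.693 and 2.771 for n = 12, and 0.8 and 3.2 for n = 16. The single point 0.5 takes away no probability.

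| Assumed true d | No label, n = 12 | No label, n = 16 |
|---|---|---|
| 0.20 | 55.2% | 54.3% |
| 0.35 | 63.5% | 67.9% |
| 0.50 | 66.0% | 72.8% |
| 0.65 | 59.4% | 64.5% |
| 0.80 | 45.8% | 47.2% |

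The range is 46% to 73%.

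**Step 4: a more generous reading.** Suppose d is rounded to one decimal before labelling, so that *moderate* covers 0.45 to 0.55. At a true d of 0.5, 60.9% (n = 12) to 65.2% (n = 16) of results still have no label.

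**The case against.** The best defence is that the line is loosely typed shorthand for three reference points at 0.2, 0.5 and 0.8. The middle entry has no inequality sign, few analysts would leave d = 0.6 without a description, and the numerical d would be reported anyway. This limits the harm but does not remove the error. The signs on the outer two entries are the protocol's own, and a less-than sign makes 0.2 a ceiling for *small*, not a reference value. Even as reference points, the text does not say where one word gives way to the next.

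It is also fair to say that no decision depends on the labels. The success criteria in the background section speak of clinically significant improvement and do not refer to d. That stands, and it is why the point is minor. Leaving the matter to a statistical analysis plan is a weaker answer, because the protocol has already fixed the scale.

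A reader might infer two stronger points, and the protocol supports neither.

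- *That a significant result could only be large or unlabelled.* This needs a two-sided test and the SD of the change as divisor, and the protocol states neither. Under those assumptions the smallest significant |d| is 0.64 (n = 12) to 0.53 (n = 16). If d is divided by a common pre/post SD instead, that threshold is multiplied by √(2(1 − r)), where r is the pre-post correlation, which the protocol does not give. A d of 0.5 is then significant once r exceeds about 0.69 (n = 12) or 0.56 (n = 16). With a one-sided test, n = 16 and the SD of the change as divisor, the threshold is 0.44.
- *That a large sit-to-stand improvement would be called small because d is negative.* Sit to stand is timed ("In-patient participants will be timed for how long it takes them to complete 5x sit to stand"), so improvement is a fall, and a signed d of −1.0 is arithmetically below 0.2. But the protocol says that d quantifies magnitude, which naturally means absolute size, and it states no sign convention. The required means and percentage changes already show the direction.

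**Conclusion.** The scale is wrong as written, and the severity is minor. Three defects follow from the text with no assumption: zero is labelled as an effect, *moderate* is a single point, and all other values from 0.2 to 0.8 inclusive have no label.

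The frequencies are illustrations. They rest on d being the mean change over the SD of the change, on normality, on 12 to 16 completers, and on assumed true effects, since the protocol gives none. With another standardiser the percentages would change, but the gap in the scale would be the same. The significance tests, the sample size and the error rates are unaffected.

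**What to change.** Replace the labelling clause with touching bands on the absolute value, for example: |d| below 0.2 negligible; 0.2 to below 0.5 small; 0.5 to below 0.8 moderate; 0.8 or above large. The exact cut-points are a convention. What matters is that the bands meet, cover every value, and include a category below *small*.

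The cost is one sentence of analysis text, with no new data and no change to the tests or the sample size. The one downside for the sponsor is that results with |d| below 0.2, which the present text would call small, would be called negligible.
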